6.1 Primary Endpoint

Effectiveness between treatment groups (FRIENDS and CATS) will be tested by calculating the 95% confidence limits (the width of the limit =|4.20|) for the differences in symptom severity, impairment, and academic competence (child outcomes) from pre to post between children receiving FRIENDS and children receiving CATS. If the calculated differences are within the 95% limit, then we will conclude that the two interventions have an equal impact or effect on child outcomes. If any of the differences in child outcomes is/are larger than the upper limit, then we will conclude that one intervention is better than the other. The limit of |4.20| was chosen based on the distribution of the reported mean effect sizes associate with FRIENDS.

Qualitative interviews with supervisors and therapists (perceived acceptability of support strategies) will be audio-recorded, transcribed and entered into NVivo 10.0 for coding and analysis. For each interview, a codebook (of common themes related to the appropriateness and acceptability of the support they received) will be developed and trialed by three coders based on an initial reading of the transcripts, and revised through discussions and subsequent transcript reviews. Coders will meet regularly to compare coding and revise the codebook. This will yield a stable set of qualitative codes that will be used to code the transcripts. Two independent coders will then code all of the transcripts. This iterative process will be continued until consensus is reached and saturation occurs. Coder reliability will be checked quarterly using the inter-rater reliability function in NVivo.

Kappa coefficients will be computed; a minimum of .85 will be required for each code. Retraining will be conducted should rater agreement fall below .85. In order to aid with interpretation of results, IE's will randomly select an additional 35% of the interviews and code them, as a measure of inter-rater-reliability. We will conduct a structured content analysis for perceived acceptability and appropriateness. The unit of analysis is each interview. We will create a case-by-variable matrix from the codes. The matrix will have an interviewee identifier number, type of support (i.e., TT, TT+), school, agency, subject demographic information, and codes. The code cells will contain the number of times the participant emitted words or phrases pertaining to perceived acceptability and appropriateness of the support they received. Once acceptability and appropriateness are defined for each interview, percentages for acceptability (% acceptance) and appropriateness (% appropriate) out of the total number of words will be calculated. Comparison of % acceptance and % appropriate between TT, TT+ will be conducted using the Wilcoxon sum rank test.

Datasets from the REDCap and NVivo databases will be combined using the statistical software SAS. Each session will be considered to be a "case" in the qualitative database and will be assigned a unique identifying number that will link it (anonymously) to the quantitative database and individual session information such as fidelity scores.

To measure the differences of implementation between therapists whose supervisors receive TT vs. TT+, means of content fidelity will be calculated with its 95% Confidence interval. Similar analysis will be done regarding process fidelity.

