2.1 Primary Objective (or Aim)

The primary objectives of this study are:

- To compare pre- to post-treatment effectiveness of different CBT treatments (FRIENDS vs. CATS) and to compare the total cost between CATS and FRIENDS.
- To compare Train-the-Trainer (TT) to Train-the-Trainer Plus (TT+) for the implementation of CATS.

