5 STUDY EVALUATIONS AND MEASUREMENTS

5.1 Screening Measurements (Students)

Potential student participants will be screened using the SCARED. The SCARED is a 41-item questionnaire used to screen for children with anxiety disorders, using five sub-scales and a Total Score. It has excellent psychometric properties and has been used in community settings as a screening instrument for anxiety disorders. Therapists will ask students or parents to complete the SCARED if referred to or enrolled into STS Programs.

STS agencies will also be encouraged to collect information about Traumatic Life Events using the Trauma History Questionnaire (THQ). The THQ is a 23-item self-report measure for children that examines experiences with potentially traumatic events such as crime, general disaster, community violence, and sexual and physical assault using a yes/no format. For each event endorsed, respondents are asked to respond "yes" or "no" if they have experienced or witnessed the event. The THQ is used in research and clinical settings and is available in English and Spanish.

For parents who consent to the sharing of this information, the study team will collect this information, as well as the SCARED. However, the THQ will not be used as a screening tool. Students will be referred to the study solely on the basis of the SCARED.

5.2 Treatment Efficacy Evaluations (Information Collected *about* the Students enrolled in FRIENDS or CATS)

Multidimensional Anxiety Scale for Children (MASC-2). The MASC-2 is a 50-item rating scale for the assessment of anxiety symptoms in children. The MASC 2 has strong psychometric properties and is sensitive for measuring treatment effects. We will use the Total Anxiety score on the parent and child forms.

Self-Report Coping Measure for Elementary School Children (SRCM). The SRCM is a 34-item self-report measure with good psychometric properties that is used to assess children's coping strategies (Seeking Social Support, Self-Reliance/ Problem-Solving, Distancing, Internalizing, and Externalizing). The Total score for the SRCM will be used in outcome analyses.

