Children's Depression Inventory – 2^{nd} Edition (CDI-2). The CDI-2 is a child self-report 27-item instrument that measures the cognitive, affective and behavioral signs of depression. The CDI has high internal consistency, moderate retest reliability, and correlates with measures of related constructs such as self-esteem, negative cognitive attributions, and hopelessness We will use the Total CDI score.

Child Behavior Checklist (CBCL). Completed by parents, this 118-item multi-axial rating scale provides a measure of children's (ages 6-18) internalizing and externalizing difficulties, as well as social and academic competencies. Good psychometric properties have been reported. We will use the Anxious/Depressed Somatic Complaints, Rule-Breaking Behavior and Aggressive Behavior scales in outcome analyses.

Engagement versus Disaffection with Learning: Teacher & Student Report. This is a 20 item teacher and student report measure which includes four sub-scales: Behavioral Engagement, Emotional Engagement, Behavioral Disaffection and Emotional Disaffection. Validity of scores is supported by findings that teacher reports are correlated with student reports, with in vivo observations in the classroom, and with markers of self-system and social contextual processes. As such, these measures capture important features of engagement and disaffection in the classroom.

*All measures noted above are validated / standardized.

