6.3 Sample Size and Power

Number of students and statistical power. It is anticipated that a total of 284 (142 students per treatment protocol) will complete the proposed study. The published reported effect size of FRIENDS has been estimated to equal 0.56 (cohen's *d*). In testing for equivalence of FRIENDS and CATS, using two one-sided tests with sample sizes of 142 in FRIENDS and 142 in CATS achieves 88% power at a 5% significance level when the true difference between the means is 0 (null hypothesis), the standard deviation of the differences in means is assumed to be 11, and the equivalence limits are -4.20 and 4.20.

Number of therapist and statistical power. To compare TT to TT+ for the implementation of CATS (H2a), with 30 therapists in TT and 30 in TT+ achieve 86% power to detect a

difference of 8% between the null hypothesis that both group means are 80% (content fidelity) and the alternative hypothesis that the mean of group TT is 80% with estimated group standard deviations of 10 and 10 (an estimated effect size=.8) and with a significance level (alpha) of 0.05 using a two-sided two-sample t-test. Similarly, group sample sizes of 30 and 30 achieve 84% power to detect a difference of 0.7 in process fidelity between the null hypothesis that both group means are 4 and the alternative hypothesis that the mean of group TT+ is 4.7 with estimated groups standard deviations of 0.9 and 0.9 (an estimated ES= .78) and with a significance level (alpha) of 0.05 using a two-sided two-sample t-test.

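### Section 6.1 judges three child constructs by one unitless limit of |4.20|, tied to no score and no primary outcome, so the FRIENDS–CATS verdict is not defined

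*Combined protocol and SAP*

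**What the plan says.** Section 6.1 (Primary Endpoint) compares FRIENDS with CATS on "differences in symptom severity, impairment, and academic competence (child outcomes) from pre to post between children receiving FRIENDS and children receiving CATS". The verdict has two branches:

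- Equality: "If the calculated differences are within the 95% limit, then we will conclude that the two interventions have an equal impact".
- Superiority: "If any of the differences in child outcomes is/are larger than the upper limit, then we will conclude that one intervention is better".

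On the origin of the limit, Section 6.1 says: "The limit of |4.20| was chosen based on the distribution of the reported mean effect sizes associate with FRIENDS". Section 6.3 computes 88% power for two one-sided tests at 5% with 142 students per program, zero true difference, and this input: "the standard deviation of the differences in means is assumed to be 11, and the equivalence limits are -4.20 and 4.20".

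Section 2.1 gives the FRIENDS–CATS comparison as a primary objective without naming an outcome. Section 5.2 does name scores. For the MASC-2 it says "We will use the Total Anxiety score on the parent and child forms", and for the CDI-2 "We will use the Total CDI score". It also selects the SRCM total and several CBCL scales, and it describes an engagement measure with four sub-scales reported by teacher and student. Section 6 allows skewed outcomes to be transformed, for example by log or Box-Cox.

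**The concern.** A margin in raw points has meaning only on a stated scale. Sections 6.1 and 6.3 give 4.20 and 11 without a score, informant or unit, and nothing in Section 5.2 supplies the link. The gaps are these:

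- No child outcome is called primary, and no score is mapped to symptom severity, impairment or academic competence.
- No instrument in Section 5.2 is described as a measure of impairment. Section 3.1.3 mentions impairment only in general terms.
- No score is selected for academic competence. The CBCL academic domain is not among the CBCL scales chosen for analysis, and no engagement sub-scale is chosen.
- The informant for the CDI is inconsistent: child self-report in Section 5.2, but among the parent-completed forms in Section 3.2.1.
- If a score is transformed under Section 6, 4.20 has no stated meaning on the new scale.

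Section 6.1 also does not say whether point differences or confidence limits must lie within 4.20. Its 95% limits do not match the two 5% one-sided tests of Section 6.3, which correspond to a 90% interval.

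At stake is the decision rule for one of the two primary comparisons. If the score, scale and interval are settled after results are seen, the data can influence the verdict.

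**Working it through.** **Inputs.** From Section 6.3: 142 per group, limits ±4.20, SD 11, true difference 0, 5% level. From Section 6.1: 95% limits. Assumed: independent children, equally correlated scores with correlation 0 to 0.7, and any SD other than 11. The documents give no correlations and no other SD.

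**Step 1: reproduce the stated power.** SE = 11 × √(2/142) = 1.305, so 4.20/SE = 3.217. Power at zero difference = 2Φ(4.20/SE − z) − 1.

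- Two 5% one-sided tests (90% interval), z = 1.645: 2Φ(1.572) − 1 = 88.4%. The t-based figure is 88.2%. This matches the plan, with 11 read as the per-child SD.
- 95% interval, z = 1.960: 2Φ(1.257) − 1 = 79.1%. The t-based figure is 78.7%.

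**Step 2: does the plan's arithmetic reveal the scale?** 4.20/11 = 0.38 SD. The published effect of 0.56 would be 0.56 × 11 = 6.16 points if it referred to the same scale, which is not stated. Neither number identifies a score.

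**Step 3: a verdict over several scores.** The table gives the chance that every score passes at SD 11 with no true difference. It uses the normal approximation, and each range runs from correlation 0 to 0.7. Three scores means one per construct. Seven is one possible count of symptom scores in Section 5.2: MASC-2 parent and child (2), CDI (1), CBCL scales (4).

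| What must lie within ±4.20 | One score | Three scores | Seven scores |
|---|---|---|---|
| 90% CI (Section 6.3 test) | 88% | 69–77% | 42–64% |
| 95% CI (Section 6.1 limits) | 79% | 50–61% | 19–44% |
| Point difference only | 99.9% | 99.6–99.7% | 99.1–99.3% |

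For correlation 0 the entry is the one-score probability to the power of the number of scores, for example 0.884³ = 0.69.

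**Step 4: the same 4.20 at other SDs** (illustrative; one score, two 5% tests, t-based).

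| SD | 4.20 in SD units | Power |
|---|---|---|
| 10 | 0.42 | 94% |
| 11 | 0.38 | 88% |
| 15 | 0.28 | 52% |

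**Step 5: false superiority.** If better means any point difference beyond 4.20, then with seven scores at SD 11 and no true difference the chance is 1 − 0.991 = 0.9% (correlation 0) to 1 − 0.993 = 0.7% (correlation 0.7). If the whole 95% interval must lie beyond 4.20, the chance is negligible.

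**The case against.** The strongest reply is that Section 5.2 does name scores and informants, that the power figure is correct for the test it describes, and that the numerical losses depend on readings and counts the plan does not fix. Much of this stands.

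- A reader might infer that the plan names no scores at all. It does; what is missing is the link from any of them to 4.20, 11 or primary status.
- A reader might infer that the 88% is wrong. It reproduces. It simply does not describe a verdict over several scores.
- A reader might quote 42–64% as the true power. That needs both the Section 6.3 test and a count of seven. The count is uncertain: the CDI informant conflicts, and the four CBCL scales depend on reading a run-together list. If point differences decide, the loss disappears.
- A reader might infer that 4.20 was derived from SD 11. Section 6.1 attributes it to FRIENDS effect sizes; Section 6.3 only pairs the two for power.
- A reader might expect the any-difference trigger to produce many false claims of superiority. At SD 11 it does not.

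It is also fair that Section 5.2 calls the measures validated or standardized, and that Section 1.3 reports CBCL T scores for the pilot work. If every score were analysed on a standardised metric with SD near 10–11, the scale problem would largely vanish. The plan does not say so, and the missing primary outcome would remain.

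**Conclusion.** The point holds and should be fixed before analysis. Its weight rests on the undefined primary verdict, which follows from the text alone: one unitless limit covers three constructs, two of them have no selected score, no primary child outcome is named, and the deciding quantity is not stated.

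The calculations show how much is left open; they are not a single estimate of lost power. At the plan's own SD of 11, the chance of concluding equality with no true difference is 88% or 79% for one score, and anywhere from 19% to 99% for seven, depending on the reading. These figures assume independent children and correlations of 0 to 0.7. Results at SDs other than 11 are illustrations only.

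**What to change.** Amend Sections 6.1 and 6.3 before outcome data are examined, and record that they were unseen. Section 6 already refers to randomization in the past tense, so the timing needs stating.

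1. Name one score already collected, with informant and score type, as the primary outcome for the FRIENDS–CATS equivalence test, for example MASC-2 Total Anxiety, child form.
2. State 4.20 in that score's units with its derivation. Confirm that SD 11 applies, or restate margin and power.
3. State that equivalence is concluded only if the confidence interval lies wholly within ±4.20. Either use the 90% interval that matches Section 6.3 (88%) or keep 95% and restate power as about 79%.
4. Delete the any-difference trigger and report other child outcomes as differences with confidence intervals. If three constructs are kept, give each one named score and its own margin, require all to pass, and restate the joint power.
5. Tie impairment and academic competence to named collected scores, or remove them from the rule.
6. Keep the equivalence test on the scale in which the margin is defined.

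No new measure or visit is needed. The cost is that secondary child outcomes lose a formal verdict, and the stated power may become less favourable.

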Therapists and supervisors will be randomly assigned to one of three conditions: a) FRIENDS with Train-the-Trainer implementation strategy (i.e., Masters-level supervisors receive training by experts on conducting supervision); b) CATS with Train-the-Trainer strategy; c) CATS using the Train-the-Trainer Plus strategy (i.e., supervisors receive training and consultation by experts on conducting supervision). Effectiveness will be measured by comparing A to B; Implementation will be measured by comparing B to C. Agency therapists will conduct all treatment groups in the schools.

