3 INVESTIGATIONAL PLAN

3.1 General Schema of Study Design

This is a 3-arm, parallel group, Type 2 Hybrid (effectiveness-implementation) design. The three groups are:

- A) FRIENDS with Train-the-Trainer (TT) implementation strategy (supervisors participate in training workshops on conducting supervision)
- B) CATS with TT strategy
- C) CATS using the Train-the-Trainer *Plus* (TT+) strategy (supervisors participate in training workshop and receive further consultation on conducting supervision).

The effectiveness part of the trial will compare A-B (different treatments); the implementation part of the trial will compare B-C (same treatment, different implementation strategies).

Agency therapists will conduct all treatment groups. At the outset of the study, therapists will be randomly assigned to condition (A, B, C).

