Given agency structure and high staff turnover rate, consented therapists and supervisors may switch roles in an additional study year dependent on randomized study arm. Similar to procedure stated above, any therapist or supervisor that switches a role in the study in condition A or B can participate in any other condition. If the participant is in condition C, then they can only participate in condition C regardless of a change in school or agency during the duration of the study.

We expect each of the therapists to run one intervention group each per year and we expect each group to be composed of 4-6 eligible and consenting students. Therapists can run a second group if time permits but is not expected for participation. Therefore, we expect to enroll 360 students in the intervention sessions.

Given that some referred students will not meet inclusion criteria and that some will not consent or not attend group, we expect that we will need to consider 426 referred students to yield 360 participating students (based on a 15% attrition rate).

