The supervisions/consultation sessions will also be coded for interruptions and session length. Service interruption is defined as the degree to which therapists are fully available for supervision and treatment sessions. We will derive three scores averaged over the total number of sessions: a) Projected length of the session in minutes minus time spent on interruptions (e.g., answering a phone call, talking about unrelated topics); b) Number of interruptions; c) Total number of supervision / consultation and treatment sessions per group.

To measure differences between support strategies (TT vs. TT+), agency supervisors (12) and therapists (60) in all groups, including participants who did not complete a treatment group but were consented and trained to participate, will be interviewed regarding their perception of the appropriateness and acceptability of the support they receive. A study staff member will conduct open-ended, semi-structured interviews about the process, feasibility and acceptability of the type of support they receive. Interviewers will follow a script to ask questions of supervisors and therapists (e.g., "How acceptable is the level of support you received for the implementation of the FRIENDS protocol?"; "Was the supervision you received from your agency's supervisor appropriate for running groups with children?"; "Was the consultation you received from the research team appropriate for preparing you to conduct supervision with STS therapists?") These interviews will be conducted at the end of each academic year, or once the treatment groups have completed. Qualitative methods will be used because there are currently no psychometrically validated measures that address these areas.

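### The 88% power rests on 142 completers per protocol where the plan's own enrolment gives about 120 per arm (about 81%), and section 6.1 does not name the arms in its contrasts, which matters most for the interviews

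*Combined protocol and SAP*

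**What the plan says.** **Design.** The trial has three arms: A is FRIENDS with TT, B is CATS with TT, and C is CATS with TT+. The abstract states: "Effectiveness will be measured by comparing A to B; Implementation will be measured by comparing B to C". Section 3.1 repeats it: "The effectiveness part of the trial will compare A-B (different treatments); the implementation part of the trial will compare B-C".

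**Analysis.** Section 6.1 describes the effectiveness comparison as pre–post differences "from pre to post between children receiving FRIENDS and children receiving CATS". It describes the fidelity comparison as TT against TT+. Neither sentence names an arm.

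**Interviews.** Section 5.3 covers 12 supervisors and "therapists (60) in all groups, including participants who did not complete a treatment group", and one of its sample questions asks about support for the FRIENDS protocol. The analysis matrix in section 6.1 holds an identifier, type of support (TT or TT+), school, agency, demographics and codes. The test is then given as: "Comparison of % acceptance and % appropriate between TT, TT+ will be conducted using the Wilcoxon sum rank test".

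**Sample size.** Section 6.3 anticipates "a total of 284 (142 students per treatment protocol") as completers. From these it derives 88% power for two one-sided tests at the 5% level, with SD 11, limits ±4.20 and a true difference of 0. For support, it compares TT with TT+ within CATS, using 30 therapists per group. Section 3.2.2 says "we expect to enroll 360 students in the intervention sessions", from 426 referred, citing 15% attrition. Section 8.1.1 recruits 6 therapists per arm per year for five years, 90 in total.

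**The concern.** FRIENDS is given only in arm A. If 360 students are spread evenly over three arms, the expected FRIENDS enrolment is below the 142 completers that the power statement needs, before any student is lost. The equivalence test would then have less power than the plan reports.

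The labels raise a different problem. CATS is delivered in two arms and TT is used in two arms, so a contrast named only by label does not say which arms go in. Adding arm C to CATS would mix the effect of expert consultation with the effect of the treatment. Adding arm A to TT would mix views about FRIENDS into a comparison of support for CATS. These choices should be settled in the analysis section before data are seen, and should not have to be inferred from other sections.

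**Working it through.** **1. Reproduce the stated power.** With a true difference of 0, the power of the two one-sided tests is approximately 2Φ(Δ/SE − 1.645) − 1, where Δ = 4.20 and SE = 11 × √(1/n₁ + 1/n₂). These inputs come from section 6.3.

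- 142 against 142: SE = 11 × √(2/142) = 1.305; 4.20/1.305 − 1.645 = 1.572; power = 88.4%. An exact t-based calculation gives 88.2%. The stated 88% is right for that n.

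**2. Expected n per arm.** 90 therapists / 3 arms = 30 per arm. 360 students / 3 = 120 per arm. This matches 30 groups × 4 students, the bottom of the 4–6 range in section 3.2.2. Equal numbers of students per arm are assumed from equal numbers of therapists.

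**3. Power for A against B at that n.**

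| Case | n per arm | SE | Power |
|---|---|---|---|
| As stated in 6.3 | 142 | 1.305 | 88.4% |
| Expected enrolment | 120 | 1.420 | 81.1% (exact 80.8%) |
| Further 15% loss after enrolment (assumed; 120 × 0.85) | 102 | 1.540 | 72.1% (exact 71.7%) |

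None of these allows for clustering, in line with the plan's own calculation.

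**4. Where 142 may come from.** 142 × 3 = 426, which is exactly the number referred in section 3.2.2. This suggests that the per-arm share of referred students was used as the number of completers. That is an inference; the plan does not say so.

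**5. Does pooling explain 142?** No. Pooling B and C gives about 120 against 240, a 1:2 split, and FRIENDS still has only 120. The sample-size mismatch is therefore separate from the labelling.

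**6. Which arms does each contrast use?**

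- *Effectiveness:* the abstract and section 3.1 say A against B. Section 6.1 does not repeat it, and nothing in section 6 explicitly excludes C.
- *Fidelity:* section 2.1 and section 6.3 limit TT against TT+ to CATS. The 30 against 30 equals 90/3 per arm, so this is B against C. Its power figures reproduce with noncentral t: 86.1% for content (stated 86%) and 84.2% for process (stated 84%).
- *Interviews:* arm A staff are interviewed, as the scope and the FRIENDS question show. The matrix has no column for arm or protocol. As written, TT is A plus B and TT+ is C. The count of 60 therapists equals two arms of 30, whereas all three arms would give 90, so the number and the stated scope disagree.

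**7. What pooling would do, if it were done.** With equal numbers in B and C, half of any TT+ effect on child outcomes is added to the CATS estimate. The documents give no such effect. Assuming 0.1 to 0.3 SD (1.1 to 3.3 points at SD 11), the shift is 0.55 to 1.65 points, or 13% to 39% of 4.20.

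**The case against.** The strongest reply is that the contrasts are already fixed. The abstract and section 3.1 define them by arm, section 2.1 ties TT against TT+ to CATS, and section 6.3 sizes fidelity at 30 against 30. On that view section 6.1 uses shorthand. This largely stands. A reader might infer from section 6.1 that arm C is meant to enter the effectiveness test or arm A the fidelity test. The documents do not support either as a stated plan, and 142 against 142 is not the 1:2 split that pooling would produce. What remains is that section 6.1 does not say so itself.

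The reply is weaker for the interviews. School is in the matrix, so arm might be recovered. But schools are randomized again for year 5, so study year is needed too, and the test as written still groups by support type alone.

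On sample size, a reader might conclude that FRIENDS cannot reach 142. That goes too far. Groups of 4 to 6 give 120 to 180 students from 30 groups, second groups are allowed, and 142 needs about 4.7 completers per group (142/30). The conflict is with the plan's expected 360, not with what is possible.

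The 72% figure is also open to challenge. The 15% in section 3.2.2 already takes referred students to participating ones and covers ineligibility, non-consent and not attending group. Applying it again is an assumption.

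**Conclusion.** The point holds in three limited parts.

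1. **Power.** The stated 88% is not delivered by the plan's own expected enrolment. For A against B at about 120 per arm it is about 81%, and lower if students are lost after enrolment. This rests on equal students per arm, SD 11, limits ±4.20, a true difference of 0 and no clustering. A drop of about 7 percentage points is moderate, but it affects the primary test.
2. **Contrasts in section 6.1.** This is an omission of wording. The intended contrasts can be read from other sections. The possible shift of 0.55 to 1.65 points depends both on pooling that the plan does not state and on an assumed TT+ effect, so it illustrates why the wording matters and does not measure an error in the plan.
3. **Interviews.** Here the text itself mixes treatment with support strategy, and the count of 60 conflicts with the stated scope.

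A reader might link the first two parts and suppose that the label wording produced the 142. It did not, since 142 fits neither A against B nor A against B plus C at 360 students.

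**What to change.** - **Section 6.3:** reconcile 142 completers per protocol with the 360 students in section 3.2.2. State the expected number per arm, say whether it is before or after loss, and restate the A against B power: about 81% at 120 per arm before clustering, and lower with any stated loss after enrolment. If larger groups or second groups are expected to bring the number to 142, revise the 360 to match.
- **Section 6.1, effectiveness and fidelity:** define the equivalence test as arm A against arm B, and content and process fidelity as arm B against arm C.
- **Sections 5.3 and 6.1, interviews:** add arm to the matrix, run the Wilcoxon comparison as arm B against arm C, and report arm A descriptively. Reconcile the 60 therapists with the scope of all groups.

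The cost is wording and a less favourable stated power. No new data are needed.

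### Section 6.1 presents the preset 4.20 margin as a 95% confidence limit and, read literally, judges equality from the observed difference, which is not the two one-sided 5% test powered in section 6.3

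*Combined protocol and SAP*

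**What the plan says.** Section 6.1 (Primary Endpoint) says effectiveness will be tested by "calculating the 95% confidence limits (the width of the limit =|4.20"|), applied to "differences in symptom severity, impairment, and academic competence (child outcomes) from pre to post between children receiving FRIENDS and children receiving CATS". Two decision rules follow. The first is "If the calculated differences are within the 95% limit, then we will conclude that the two interventions have an equal impact". The second is "If any of the differences in child outcomes is/are larger than the upper limit, then we will conclude that one intervention is better". Section 6.1 adds that 4.20 was picked from the published effect sizes for FRIENDS, so it does not come from the trial's own data.

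Section 6.3 (Sample Size and Power) describes an equivalence test "using two one-sided tests with sample sizes of 142 in FRIENDS and 142 in CATS achieves 88% power at a 5% significance level", where "the standard deviation of the differences in means is assumed to be 11, and the equivalence limits are -4.20 and 4.20".

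Section 5.2 lists the student measures. They include the MASC-2 ("We will use the Total Anxiety score on the parent and child forms"), a coping measure, the CDI-2, several CBCL scales and an engagement measure. It does not say which of them carries the 4.20 or the SD of 11.

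**The concern.** The same number has two roles. In 6.3 it is a margin, and the data must rule out differences beyond it. In 6.1 it is labelled a confidence limit, and the quantity compared with it is the calculated difference. A confidence limit comes from the data and moves with the sample; a margin is fixed beforehand. If the two are merged, the natural reading of 6.1 is that a point estimate inside ±4.20 is enough to declare equal impact, with no allowance for sampling error.

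This rule decides the first primary objective in section 2.1. CATS has 8 sessions against 12 for FRIENDS (section 1.2.1), so a finding of equal impact would support the shorter programme. Some results would be declared equal under one section while equivalence is not shown under the other. The plan does not say which section governs, so the choice could be made after the data are seen.

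**Working it through.** **Inputs, all from section 6.3:** 142 students per arm; SD 11; limits −4.20 and 4.20; 5% for each one-sided test; true difference 0. The SD is described as that of the differences in means. It reproduces the stated power only as the per-student SD of change: as a standard error it would give a 95% half-width of 1.96 × 11 = 21.56, and equivalence could never be shown. No clustering is included, as in 6.3.

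**Standard error.** SE = 11 × √(2/142) = 1.3055, with 282 degrees of freedom.

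**Reproducing the 88%.** The normal approximation is 2Φ(4.20/SE − 1.645) − 1 = 2Φ(3.217 − 1.645) − 1 = 88.4%. The t-based calculation, integrated over the sample SD, gives 88.2%. The plan's figure is reproduced for the test that 6.3 names. (Section 6.3 calls a true difference of 0 the null hypothesis. For an equivalence test it is the value at which power is evaluated; the label changes no number.)

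**Interval widths.**
- 90% half-width: 1.650 × 1.3055 = 2.154.
- 95% half-width: 1.968 × 1.3055 = 2.570; full width 5.14.

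Neither the half-width nor the full width of the 95% interval is 4.20, in line with 6.1's own statement that the figure was chosen beforehand.

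**Largest observed difference that each rule accepts.**
- 6.1 read literally: 4.20.
- 6.3 (90% interval inside the margin): 4.20 − 2.154 = 2.05.
- Two-sided 95% interval inside the margin: 4.20 − 2.570 = 1.63.

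**Probability of declaring equality or equivalence, by true difference.** The literal rule is Φ((4.20 − d)/SE) − Φ((−4.20 − d)/SE); the other two columns are t-based.

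| True difference d | 6.1 literal | 6.3 test | 95% interval inside |
|---|---|---|---|
| 0 | 99.9% | 88.2% | 78.7% |
| 2 | 95.4% | 51.4% | 38.7% |
| 3 | 82.1% | 23.3% | 14.8% |
| 4.20 | 50.0% | 5.0% | 2.5% |

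**Example.** For an observed difference of 3.0, t = 3.0/1.3055 = 2.30 and p = 0.022. The 90% interval is 3.0 ± 2.154, or 0.85 to 5.15. Literal 6.1 calls this equal. The 6.3 test does not show equivalence, because the interval passes 4.20, and the difference from zero is significant at 5%.

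**The rule for one intervention being better.** At an observed 4.20, t = 4.20/1.3055 = 3.22 and p = 0.0014. If the true difference is 0, the chance of exceeding 4.20 in either direction is 2 × (1 − Φ(3.217)) = 0.13%.

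**The case against.** The strongest reply is that the two sections should be read together. Section 6.1 begins by calculating confidence limits, a step with no purpose if only the point estimate counts. Section 6.3 names the test outright. Two one-sided 5% tests correspond to two one-sided 95% limits, so the 95% in 6.1 might refer to those, and the documents would then contain one coherent procedure. This is a fair account of what the authors may have intended, and it limits the finding: the 50% error belongs to the literal reading only. It is also generic, since any point-estimate rule gives about 50% at its own cut-off. But 6.1 does not state this reading; it makes 4.20 itself the limit and compares the calculated difference with it. The other natural repair, a two-sided 95% interval inside the margin, gives 79% rather than 88%. An analyst would still have to choose.

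Three stronger inferences are not supported:

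- **That the 88% power is wrong.** It is right for the 6.3 test on the 6.3 inputs.
- **That the rule for declaring one intervention better inflates false positives.** At the plan's standard error it is stricter than a 5% test. It would lose that protection only if the SE exceeded 4.20/1.968 = 2.13, a variance inflation of (2.134/1.3055)² = 2.67.
- **That an error rate or power can be given for several outcomes together.** The documents give no number of primary outcomes, no correlations, and no SD or margin for each scale, so any such figure would be illustrative.

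It also stands that the figures are best-case. Schools are randomised (section 8.1.1), and clustering would widen every interval. The 360 students in section 3.2.2, split evenly over three arms, are 120 per arm, where the same test has about 81% power. Neither point removes the mismatch.

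**Conclusion.** The point holds as an inconsistency between the decision rule in 6.1 and the test in 6.3. It is wrong as written, not merely lacking detail: an observed difference between about 2.05 and 4.20 is equal impact under literal 6.1, while under 6.3 equivalence is not shown. At a true difference equal to the margin, the chance of wrongly declaring equality is about 50% under literal 6.1 and 5% under 6.3.

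The cut-offs and powers rest on 6.3's inputs only: 142 per arm, SD 11 per student, one outcome and no clustering. The 50% barely depends on SD or sample size, but it is conditional on the literal reading. A reader might take it as the error rate of the trial's primary analysis; the documents do not support that, because 6.3 specifies a sound test and 6.1 is ambiguous. The sample-size calculation is not faulted here.

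**What to change.** In section 6.1:

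- Call ±4.20 the equivalence margin, and drop its description as a confidence limit.
- Name the child outcome and the scale to which the margin and the SD of 11 apply.
- State that equivalence is concluded only if the whole 90% confidence interval for the A–B difference in pre-to-post change lies between −4.20 and 4.20 (two one-sided 5% tests, as in 6.3).
- State that failing this does not by itself show that one intervention is better. A result that supports neither equivalence nor a difference is inconclusive, and any claim that one is better is reported with its confidence interval.

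If the sponsor prefers a two-sided 95% interval for equivalence, restate the power in 6.3 as about 79% under the same inputs; about 171 per arm would be needed to keep 88%. If equivalence must hold on more than one outcome, recompute the 6.3 power for that rule.

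The cost is wording plus the sponsor's decision on which outcome carries the margin. With one outcome and the 90% interval, matching 6.1 to 6.3 needs no extra data or participants. It should be settled before outcome data are analysed.
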